The differences in ofatumumab doses between the arms of the study are considered acceptable because less ofatumumab is being administered in the investigational combination arm (Arm A) than is being administered in the control single-agent arm (Arm B). If the treatment effect is better in Arm A than in Arm B despite this difference, the results will provide particularly convincing testament to the merits of the idelalisib/ofatumumab combination.

Because of the difference in ofatumumab doses between the arms, both idelalisib and ofatumumab placebos would be required to blind the study. Centralized blinding is not possible because an ofatumumab placebo is not available. Attempting to blind the trial at the level of the pharmacist or nurse would be procedurally insufficient for maintaining the ofatumumab blind. In addition, there would be a high likelihood of breaking the blind due to expected differences in infusion times between the arms. In view of these constraints, the investigational site and sponsor study teams will have knowledge of the treatment assignments for individual subjects. However, several steps will be taken to minimize potential bias:

- Investigational sites will not be presented with any summary data or analyses during the course of the study.
- Efficacy results will be subjected to review by an independent review committee (IRC) that will be blinded as to treatment arm (see Section 10.4.2).
- An independent data monitoring committee (DMC) will be established to review accumulating study results in closed data review sessions and provide recommendations regarding study conduct.

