### 5.3. Study Drug Administration

#### 5.3.1. Overview of Dosing Regimen

[Table 5-1](#) provides information regarding the planned dosing regimen. All subjects will receive the recommended premedication ~30 to ~60 minutes (or per institution-specific standard) before the ofatumumab infusion. In Arm A, idelalisib will be administered together with the premedication ~30 to ~60 minutes before the ofatumumab infusions. For both treatment arms

(Arm A and Arm B) the first infusion of ofatumumab will be administered at a dose of 300 mg. At each of Visits 3 through 13, subjects on both arms will be given the recommended premedications, and ofatumumab will be infused at a dose of 1,000 mg (Arm A) or 2,000 mg (Arm B).

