**Table 5-3. Study Drug (Ofatumumab) Infusion Rates**

Interval After Start of Infusion, min	Arm A		Arm B		
	Infusion 1 (300 mg), ml/hr	Infusion 2-12 (1,000 mg), ml/hr	Infusion 1 (300 mg), ml/hr	Infusion 2 (2,000 mg), ml/hr	Infusion 3-12 (2,000 mg), ml/hr
0-30	12	25	12	12	25
31-60	25	50	25	25	50
61-90	50	100	50	50	100
91-120	100	200	100	100	200
> 120	200	400	200	200	400

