### 9.3.2. Data Handling Conventions

#### 9.3.2.1. General Methods

By-subject listings will be created for important variables from each eCRF module. Summary tables for continuous variables will contain the following statistics: N (number in analysis set), n (number with data), mean, and standard deviation, 95% confidence intervals (CIs) on the mean, median, minimum, and maximum. Summary tables for categorical variables will include: N, n, percentage, and 95% CIs on the percentage. Unless otherwise indicated, 95% CIs for binary variables will be calculated using the binomial distribution (exact method) and will be 2-sided. Data will be described and summarized by relevant treatment arm, analysis set, and timepoint. As appropriate, changes from baseline to each subsequent timepoint will be described and summarized by treatment arm. Similarly, as appropriate, the best change from baseline during the study will also be described and summarized by treatment arm. Graphical techniques (eg, waterfall plots, Kaplan-Meier curves, line plots) may be used when such methods are appropriate and informative.

The baseline value used in each analysis will be the last (most recent) pre-treatment value. Subjects with discrepancies between the stratification factor values at randomization and the actual values as documented on data review will be categorized in the analyses according to the actual values. In the situation that there is insufficient information in a stratum (ie, if there are < 6 subjects or there is no informative event in a stratum), that stratum will be pooled with the smallest adjacent stratum for stratified analyses; the smallest stratum is defined as that stratum having the fewest number of subjects or the fewest number of events in case the former is a tie and the adjacent stratum is defined as a stratum having 2 factors of the 3 at the same level. Data from all sites will be pooled for all analyses. Analyses will be based upon the observed data unless methods for handling missing data are specified. If there is a significant degree of non-normality, analyses may be performed on log-transformed data or nonparametric tests may be applied, as appropriate.

Unless otherwise specified, all analyses will be 2-sided at the 0.05 level of significance.

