The severity of ofatumumab-related infusion reactions and of the total durations of ofatumumab infusions will be compared between treatment arms to determine whether idelalisib pretreatment modifies the magnitude of such events or alters the length of the ofatumumab infusion due to such events; the focus of this analysis will be on the first 2 ofatumumab infusions (ie, those on Study Day 1 and on Day 8). However, assessment of infusion reaction severity and duration will be performed for all 12 planned infusions of ofatumumab. Comparisons will be done using the Chi-square test for severity grade and the Wilcoxon rank-sum test for infusion duration.

Separate listings and summaries will be prepared for long-term follow-up safety data.

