### 9.5. Sample Size

Based on data from the Phase 2 pivotal study ofatumumab {[Wierda 2010](#)} and considering the population of subjects to be enrolled to this study, it is reasonable to assume that administration of ofatumumab to subjects with previously treated CLL in Arm B of this trial will result in a median PFS of ~8 months. An improvement in median PFS from 8 months to 14 months due to the addition of idelalisib to ofatumumab in Arm A of the study would correspond to a benefit ratio of 1.75 (hazard ratio 0.57).

It is assumed that PFS times are exponentially distributed in each of the 2 arms. With a hazard ratio equal to 1 under the null hypothesis of no difference between the 2 treatment arms and a hazard ratio of 0.57 under the alternative hypothesis of superiority of the idelalisib-containing combination, 129 events (definitive CLL progressions or deaths) are required to achieve a power of >0.85 based on a log-rank test with a 2-sided significance level of 0.05. Further assuming a planned accrual period of 12 months (with approximately half of the subjects enrolled during the initial 60% of the accrual period, and the remaining half of the subjects enrolled during the last 40% of the accrual period), a minimum follow-up period of 12 months, and an expectation that 10% of subjects will be lost to follow-up (5% during the accrual period and 5% during the follow-up period), and to ensure the primary analysis on PFS will be performed before or at the planned minimum 12-month follow-up period, 170 subjects will be enrolled into Arm A and 85 subjects will be enrolled into Arm B in order to achieve the expected number of events by the end of the planned minimum 12-month follow-up period. If the planned subject enrollment does not appear adequate to accrue the expected number of events within the proposed follow-up period, the sample size may be adjusted upward.

It is expected that there will be approximately 65 deaths at the time of final analysis. This would provide ~85% power to detect a HR of 0.45 for overall survival based on a log-rank test at 2-sided alpha level of 0.03.

The resulting safety data set provided by the idelalisib-treated subjects (N=170) compares favorably with the safety data set derived from the initial pivotal registration trials for ofatumumab (N=138) {[Wierda 2010](#)}, oral fludarabine (N=78) {[Boogaerts 2001](#)}, or alemtuzumab (N=93) {[Keating 2002a](#)}.

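### The Day 8 infusion comparison cannot show an idelalisib effect: the arms differ by protocol in ofatumumab dose and rate, so the duration test will reject anyway

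*Protocol*

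**What the plan says.** Section 9.4.2.4 compares the severity of ofatumumab infusion reactions and the total duration of infusions between arms "to determine whether idelalisib pretreatment modifies the magnitude of such events or alters the length of the ofatumumab infusion due to such events". It states that "the focus of this analysis will be on the first 2 ofatumumab infusions (ie, those on Study Day 1 and on Day 8"), while also covering all 12 infusions. The tests are fixed in the same paragraph: "Comparisons will be done using the Chi-square test for severity grade and the Wilcoxon rank-sum test for infusion duration". There is no adjustment for ofatumumab dose or rate, and Section 9.3.2.1 sets the default that "all analyses will be 2-sided at the 0.05 level of significance".

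On Day 1 the arms match. In both, "the first infusion of ofatumumab will be administered at a dose of 300 mg" (Section 5.3.1), with identical rates in Table 5-3. On Day 8 Arm A moves to 1,000 mg and Arm B to 2,000 mg. Table 5-3 puts Arm A on its faster column ("Infusion 2-12 (1,000 mg), ml/hr"), while Arm B has a separate, slower column for infusion 2. Section 2.2 gives "expected differences in infusion times between the arms" as one reason why blinding is not feasible.

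**The concern.** The analysis attributes any between-arm difference to idelalisib. On Day 8 idelalisib is only one of three differences; the others are ofatumumab dose and infusion rate. Section 5.10 itself says the lower ofatumumab dose in Arm A may reduce the frequency and severity of infusion reactions and shorten administration. Those are the two outcomes that Section 9.4.2.4 then credits to idelalisib.

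The variable also misses the question. The question is about lengthening caused by reactions, but the test uses total duration, which includes scheduled time. The trial could report a highly significant shortening of infusion with idelalisib that comes from the rate table, and it could do so even if idelalisib made reactions worse.

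**Working it through.** The protocol states no infusion duration and no power for this comparison, so there is no figure to reproduce.

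**Inputs**
- Rates (Table 5-3), four 30-minute steps and then a final rate. Slow column: 12, 25, 50, 100, then 200 mL/h. Fast column: 25, 50, 100, 200, then 400 mL/h. Infusion 1 uses the slow column in both arms. At infusion 2 Arm A uses the fast column and Arm B the slow one. At infusions 3 to 12 both use the fast column.
- Rates are ceilings (Section 5.3.3.2).
- Volume (Section 5.2.2.5): each dose is made up to 1,000 mL by removing and replacing equal volumes.
- Sample size (Section 9.5): "170 subjects will be enrolled into Arm A and 85 subjects will be enrolled into Arm B".
- Reaction rates in the earlier Phase 2 trial (Section 5.3.3.3): 44% at infusion 1 and 29% at infusion 2.

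**Scheduled, reaction-free duration** = 2 h + (1,000 − volume given in the first 2 h) / final rate.
- Fast column: 0.5 × (25 + 50 + 100 + 200) = 187.5 mL, then 812.5 / 400 = 2.03 h. Total 4.03 h.
- Slow column: 0.5 × (12 + 25 + 50 + 100) = 93.5 mL, then 906.5 / 200 = 4.53 h. Total 6.53 h.

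| Infusion | Arm A | Arm B | Built-in difference |
|---|---|---|---|
| 1 (300 mg both) | 6.53 h | 6.53 h | 0 |
| 2 (1,000 vs 2,000 mg) | 4.03 h | 6.53 h | 2.50 h (2.50 / 4.03 = 62%) |
| 3 to 12 (1,000 vs 2,000 mg) | 4.03 h | 4.03 h | 0 |

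**Chance of rejecting on Day 8 from the schedule alone.** Power ≈ Φ(2.50 / [SD × √((1/170 + 1/85) × π/3)] − 1.96), where π/3 allows for Wilcoxon efficiency. The SD is an assumption, so a range is shown:

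| SD of duration | Power |
|---|---|
| 0.5 to 3 h | > 0.999 |
| 4 h | 0.996 |
| 5 h | 0.957 |
| 6 h | 0.866 |

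**Simulation.** 2,000 trials of 170 vs 85 subjects, two-sided rank-sum test at 0.05. Duration = schedule + exponential delay in reactors + exponential noise. Delay and noise are assumptions.
- Day 8, no idelalisib effect, 29% reactions in both arms, mean delay 1 to 4 h, mean noise 0.1 to 2 h: 100% rejection in every setting.
- Day 8, mean delay 2 h, mean noise 0.5 h: still 100% rejection if idelalisib abolishes Arm A reactions, and also if it raises them to 58%, 87% or 100%.
- Same setting, every Arm A infusion lengthened by 2.25 h: 92% rejection. Lengthened by 2.5 h: 5.6%, because a real effect then cancels the schedule.
- Day 1, equal schedules, 44% reactions in both arms, no effect: 5.0%, the nominal level.

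**Severity on Day 8.** Arm A is 1 mg/mL and Arm B 2 mg/mL, so scheduled delivery is 25/50/100/200/400 mg/h against 24/50/100/200/400 mg/h. At 2 h each arm has received about 187 mg. Drug delivery rate is therefore nearly matched. What differs is total dose and Arm B's extra 2.5 h of exposure. From infusion 3 Arm B has twice the dose and twice the mg/h.

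**The case against.** The strongest reply accepts the Day 8 duration arithmetic and argues that the defect is narrow.

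- **Severity is not confounded by rate on Day 8.** This stands. Delivery in mg/h is almost equal, and Section 5.3.3.3 places reaction onset at 30 to 120 minutes, when scheduled exposure is nearly the same. The confounder for severity is dose, which Section 5.10 says may matter. The Chi-square test is not certain to reject, but a difference in either direction still could not be assigned to idelalisib.
- **Infusion 1 follows only a single idelalisib dose,** given about 30 to 60 minutes earlier, whereas Day 8 follows a week of dosing. This also stands and is a real cost of the fix. It does not make Day 8 interpretable.
- **Section 5.3.3.2 says later infusions can start at 25 mL/h, while Table 5-3 gives 12 mL/h for Arm B infusion 2.** These passages contradict each other and must be reconciled. If both arms followed one mL/h column, the duration gap would vanish, but doses of 1,000 and 2,000 mg would remain, now with twice the mg/h in Arm B. Day 8 would still not isolate idelalisib.
- **This is a safety comparison outside the primary and the five sequentially tested endpoints.** True. It limits the consequence without correcting the stated inference.

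**Conclusion.** The concern holds. As written, the Day 8 duration test measures the rate table: a scheduled difference of 2.50 h makes rejection near certain with no idelalisib effect, and also with a sizeable beneficial or harmful one. This rests on Arm B following its Table 5-3 column at infusion 2 and on an SD of duration up to about 5 h (power at least 0.957); at 6 h the power is still 0.866. The Day 8 severity comparison is confounded by ofatumumab dose without being bound to reject. Day 1 is sound. The protocol itself fixes the causal question, the infusions and the tests, so this is not detail left to a later plan. It should be corrected, but no primary or error-controlled conclusion depends on it.

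**What to change.** Amend Section 9.4.2.4, and the analysis plan to match:

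1. Base the inference about idelalisib pretreatment on infusion 1 only, for both severity and duration, and state that it concerns the first idelalisib dose.
2. For infusion 2 onward, analyse actual minus Table 5-3 scheduled duration or, if the case report form captures it, whether a reaction led to interruption or slowing.
3. Label every severity and duration comparison from infusion 2 onward as between regimens, not as an effect of idelalisib. The label is needed even for actual minus scheduled time, because dose still differs and, under Section 5.3.3.3, a restart at half the previous rate adds more time when that rate is lower.
4. Reconcile Section 5.3.3.2 with Table 5-3 on the starting rate for Arm B infusion 2, since the scheduled time depends on it.

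The cost is wording. Worst reaction severity and total infusion duration are already recorded at each infusion. The sponsor gives up a Day 8 p-value for idelalisib and has no clean answer on pretreatment after a week of dosing, which this design cannot supply.

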#### **5.1.2. Randomization and Stratification**

After a subject has completed the necessary screening assessments and has been confirmed to be eligible, the subject can be randomized into the study. In order to obtain a treatment arm assignment for a subject, a site representative will access the IWRS and supply the system with the required information.

Subjects will be randomized in a 2:1 ratio to either of the following treatment assignments:

- Arm A: Idelalisib + ofatumumab (1,000-mg dosing regimen)
- Arm B: Ofatumumab (2,000-mg dosing regimen)

In order to balance treatment allocation by potentially important predictive factors, a fixed-block centralized randomization will allocate subjects within the 8 strata as defined by the intersection of the following 3 binary stratification factors:

- 17p deletion and/or TP53 mutation in CLL cells: either vs neither (or indeterminate)
- Immunoglobulin heavy chain variable region (IgHV) mutation: unmutated (or IgHV3-21) vs mutated (or indeterminate)
- Disease status: refractory (CLL progression < 6 months from completion of prior therapy) vs relapsed (CLL progression ≥ 6 months from completion of prior therapy)

The IWRS will assign kit numbers for dispensing of study drug. It is anticipated that subjects will usually begin study drug immediately after randomization at Visit 2 of the study. In case of administrative delays, every attempt should be made to initiate study drug as soon as possible, but no more than 7 days from randomization.

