#### Study Treatment Administration

Study drug administration (Arm A)	First dose of idelalisib to be administered to the subject in clinic (with recording of the date and actual clock time of the study drug administration)
Pretreatment	Oral antipyretic, oral or IV antihistamine, and IV corticosteroid to be administered to the subject at the same time as idelalisib (Arm A) and ~30 to ~60 minutes prior to ofatumumab infusion
Ofatumumab infusion	Ofatumumab, 300 mg, to be administered by intravenous infusion ~30 to ~60 minutes after pretreatment
Ofatumumab infusion severity and duration assessment	Worst severity of ofatumumab infusion reaction to be graded and total duration of ofatumumab infusion to be recorded. Following the ofatumumab infusion, monitor the subject for infusion toxicity, including vital signs, ~every 15 minutes for ~1 hour

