### 9.4.2.4. Adverse Events

All adverse events will be listed. The focus of adverse event summarization will be on treatment-emergent adverse events. A treatment-emergent adverse event is defined as an adverse event that occurs or worsens in the period from the first dose of study treatment (idelalisib or ofatumumab) to 30 days after the last dose of study drug.

Adverse events will be classified using MedDRA (<http://www.meddra.org>) with descriptions by System Organ Class, High-Level Group Term, High-Level Term, Preferred Term, and Lower-Level Term. The severity of adverse events will be graded by the investigator according to the CTCAE, Version 4.03 ([http://evs.nci.nih.gov/ftp1/CTCAE/CTCAE\\_4.03\\_2010-06-14\\_QuickReference\\_8.5x11.pdf](http://evs.nci.nih.gov/ftp1/CTCAE/CTCAE_4.03_2010-06-14_QuickReference_8.5x11.pdf)), whenever possible. If a CTCAE criterion does not exist for a specific type of adverse event, the grade corresponding to the appropriate adjective will be used

by the investigator to describe the maximum intensity of the adverse event: Grade 1 (mild), Grade 2 (moderate), Grade 3 (severe), Grade 4 (life threatening), or Grade 5 (fatal). The relationship of the adverse event to the study drug will be categorized as related or unrelated.

Separate listings and summaries will be prepared for the following types of treatment-emergent adverse events:

- Study-treatment-related (idelalisib or ofatumumab) adverse events
- Adverse events that are Grade  $\geq 3$  in severity
- Adverse events leading to study treatment (idelalisib or ofatumumab) interruption and/or dose modification
- Adverse events leading to study drug (idelalisib or ofatumumab) discontinuation
- Serious adverse events (with categorization of the primary reason that the adverse event is considered serious, eg, death, hospitalization, etc)

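### The Chi-square test named for infusion-reaction grade ignores the order of the grades, so it cannot by itself show the direction of a change, and it loses power if severity shifts as a whole

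*Protocol*

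**What the plan says.** Section 9.4.2.4 (Adverse Events) sets up a between-arm comparison of infusion-reaction severity and infusion duration "to determine whether idelalisib pretreatment modifies the magnitude of such events or alters the length of the ofatumumab infusion due to such events". The focus is on infusions 1 and 2, and all 12 infusions are assessed. The tests are named in one sentence: "Comparisons will be done using the Chi-square test for severity grade and the Wilcoxon rank-sum test for infusion duration".

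The outcome is defined in the visit tables, for example Table 6-2: "Worst severity of ofatumumab infusion reaction to be graded and total duration of ofatumumab infusion to be recorded". Grades follow CTCAE, from Grade 1 (mild) to Grade 5 (fatal), as set out in Sections 8.2.2 and 9.4.2.4. The default significance level is in Section 9.3.2.1: "Unless otherwise specified, all analyses will be 2-sided at the 0.05 level of significance".

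The protocol names no trend, row-mean-score or other ordinal form of the Chi-square test, and it does not say that the grades are dichotomised. It gives no power, effect size or expected grade distribution for this comparison.

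**The concern.** The question is about magnitude, and magnitude on this outcome is position on an ordered scale. A general Chi-square statistic on the arm-by-grade table is unchanged if the grade labels are shuffled. A small p-value therefore says that the two distributions differ, and does not say that one arm had more or less severe reactions. The same sentence already uses a rank test for duration, so an ordinal method is available within the plan.

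Two things are at stake. One is interpretation: direction has to be read informally from the table. The other is efficiency: if severity shifts as a whole, a test with several degrees of freedom spreads its power over patterns that are not the one of interest. Infusion 1 is the cleanest comparison, because both arms receive 300 mg on the same rate schedule (Table 5-3).

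**Working it through.** The protocol states no power figure for this comparison, so there is none to reproduce.

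**Inputs from the protocol.**
- Sample sizes, Section 9.5: "170 subjects will be enrolled into Arm A and 85 subjects will be enrolled into Arm B".
- Any reaction at infusion 1: 44%. At infusion 2: 29%. Both come from the pivotal Phase 2 ofatumumab trial as reported in Section 5.3.3.3.
- Two-sided 0.05, Section 9.3.2.1.

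**Assumed, not in the protocol.** The split of the 44% across grades. The main split for Arm B is none 56%, G1 15%, G2 20%, G3 or higher 9%. Three others were tried: 56/20/18/6 (four categories), and 56/20/18/5/1 and 56/12/24/7/1 (five categories).

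**Tests.** Pearson Chi-square on the 2 x K grade table (K − 1 degrees of freedom: 3 or 4 here) against the tie-corrected Wilcoxon rank-sum test on the same grades with no reaction scored 0. Power is by simulation, with 20,000 to 40,000 trials per scenario.

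**Common shift.** Under proportional odds, the odds of being at or below each grade in Arm A are the Arm B odds divided by the odds ratio (OR). For OR 0.50 on the main split:
- none: 0.56/0.44 = 1.273, then 1.273/0.50 = 2.545, giving 0.718
- G1 or lower: 0.71/0.29 = 2.448, then 4.897, giving 0.830
- G2 or lower: 0.91/0.09 = 10.11, then 20.22, giving 0.953

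The any-reaction rate in Arm A is then 28%, and G3 or higher is 4.7%.

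| OR, infusion 1, main split | Chi-square | Wilcoxon | Gap (points) |
|---|---|---|---|
| 1 (no effect) | 5% | 5% | 0 |
| 0.60 | 36% | 49% | 13 |
| 0.50 | 59% | 73% | 14 |
| 0.45 | 71% | 84% | 13 |
| 0.40 | 82% | 91% | 9 |

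With five categories at OR 0.50 the figures are 56% v 74%, a gap of 18. Over all four splits and ORs 0.40 to 0.60 the gap is 9 to 18 points. At OR 0.33 on the main split it falls to about 4. At infusion 2 (29% any reaction, two assumed splits) it is about 9 to 17 points for ORs from 0.67 to 0.40. Under no effect, both tests reject at or below 5% up to simulation error.

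**Other patterns, infusion 1, main split.** In the last four rows the any-reaction rate stays at 44%.

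| Change in Arm A | Chi-square | Wilcoxon |
|---|---|---|
| Every reaction has a 30% chance of dropping one grade | 14% | 15% |
| Every reaction has a 50% chance of dropping one grade | 35% | 33% |
| Half of G2 become G1 | 58% | 9% |
| Half of G2 and half of G3 drop one grade | 50% | 12% |
| Half of G2 and half of G3 become G1 | 82% | 17% |
| Two thirds of G3 become G2 | 44% | 6% |

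In the first two rows G1 reactions that drop one grade become no reaction. For the 50% row the any-reaction rate is 0.44 − 0.5 × 0.15 = 36.5%.

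**The case against.** The strongest case for the plan is that the stated question is whether magnitude is modified, with no direction given, and that it naturally includes reactions becoming milder without becoming rarer. A Grade 2 reaction that becomes Grade 1 is a true reduction in severity. With 56% of subjects scored 0, the Wilcoxon test is driven largely by reaction v no reaction and can miss that pattern badly, as the last four rows show. The Chi-square is also valid, the comparison lies outside the controlled sequence in Section 9.4.1.6, a grade table would show direction to the eye, and the categories may be settled in the SAP.

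Most of this stands. It rules out dropping the Chi-square outright, and it rules out quoting one figure as the price of the plan. Two points remain. Whatever its power, an unordered test does not answer a question about position on an ordered scale. And the protocol's own rationale (Section 5.10) anticipates that infusion reactions will become both less frequent and less severe in Arm A, although it attributes this to the lower ofatumumab dose. When both fall together by a common shift, the rank test does better.

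A reader might infer that the plan loses 9 to 18 points of power whatever the effect, or that the Wilcoxon test is better throughout. The documents do not support either: they give no grade distribution and no expected effect, and the ordering of the two tests depends on both.

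**Conclusion.** The concern holds in a limited form. The named test ignores the order of the grades and cannot by itself establish direction. The loss of about 9 to 18 points at infusion 1 rests on a proportional-odds shift with OR about 0.40 to 0.60, on assumed grade splits, on the 44% reaction rate from the earlier trial, and on all 170 and 85 subjects contributing. Without a common shift the loss can be nil or become a gain for the Chi-square.

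This is a matter of efficiency and interpretation in an exploratory safety comparison. It introduces no bias, does not inflate type I error, and touches no primary or secondary endpoint. At infusion 2 the ofatumumab dose and starting rate differ by arm (Table 5-3: 1,000 mg from 25 ml/hr v 2,000 mg from 12 ml/hr), so no choice of test isolates the effect of idelalisib there. The point is a minor improvement.

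**What to change.** In Section 9.4.2.4, make the Wilcoxon rank-sum test on worst grade, with no reaction scored 0, the main severity comparison at each of the two focus infusions. Report alongside it the grade table by arm and the proportion with Grade 3 or higher. Keep the Chi-square as a supportive test, so that milder-but-not-rarer patterns are not missed.

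A row-mean-score Cochran-Mantel-Haenszel test stratified by the randomisation factors is an alternative. It is not equivalent to the unstratified Wilcoxon test, because its result depends on the scores chosen and on the eight strata; if it is preferred, the scores should be stated.

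The cost is a change of wording and one extra exploratory p-value per focus infusion. No new data are needed.
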